6.6.5. End of Treatment

At the End of Treatment patients will undergo:

- A brief symptom driven physical examination
- Vital signs: blood pressure, heart rate, respiratory rate, and oral temperature (after seated or supine for 5 minutes) and SpO₂
- 12-lead ECG (after supine for 5 minutes)
- Blood samples for hematology, clinical chemistry, urinalysis, and pregnancy test
- Patient Global Assessment
- AEs
- Concomitant medication use

End of Treatment assessments do not follow a +/- 10 minute window, but just need to be completed prior to discharge

6.6.6. Follow up

A final safety assessment will be conducted on Day 14 (\pm 2 days) from the first dose via a telephone call to check on general well-being, including spontaneous reports of adverse events and concomitant medications.

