
Surgery:
 
Surgery will occur on Day 0. Sites will follow their standard operating procedures.
 
Treatment Period/Post Surgery:
 
Patients will receive their first dose of study medication (T0) within 8 hours of meeting the postsurgical eligibility criteria. Patients will be dosed at Hour T0, T2, T4, and then every 4 hours thereafter, for a total of up to 43 doses administered over the 168-hour treatment period (with the last possible dose at Hour 164). Treatment is anticipated to occur from Hours 0 to 48, and may extend through to Hour 168. .
 
Safety will be assessed by recording vital signs including: ECG's, respiratory rate, heart rate, pulse oximetry (SpO₂), temperature, and blood pressure as per the schedule of events.
 
A Patient Global Assessment (PGA – Appendix 1) of efficacy will be obtained at Hour 24 and End of Treatment. If the patient continues treatment beyond Hour 24, PGA will be conducted at Hour 24 and End of Treatment (total of 2 PGAs). If the patient ends treatment prior to Hour 24, PGA will be conducted as part of the End of Treatment visit (total of 1 PGA).
 
At the End of Treatment assessment, patients will undergo a brief physical examination, vital signs measurements, ECG, PGA and clinical laboratory evaluations for safety. AEs and concomitant medication use will be recorded.
 
Follow up:
 
A final safety assessment will be conducted on Day 14 (± 2 days) from the first dose via a telephone call to check on general well-being, including spontaneous reports of adverse events and concomitant medications.
 
Concomitant Medication:
 
Medications deemed necessary for the patient's welfare are permitted. The following drugs are EXCLUDED from use:
 
 • Moderate or strong inhibitors of CYP3A4 or CYP2D, inducers of CYP3A4, drugs which may increase serotonergic tone including SSRIs, SNRIs, tricyclic antidepressants, trazodone, cyclobenzaprine triptans, 5-HT₃ antagonists including ondansetron, and amphetamines; and drugs which may lower seizure threshold. • Any opioid based analgesic (post dosing). 
Postoperative adverse events (AEs) such as nausea, vomiting and pruritus should be managed using standard of care, excluding medications specifically noted in the study protocol.

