
Protocol AVE-901-104 Phase 3 Open-Label Safety Study
Avenue Therapeutics, Inc.

Tramadol Infusion
August 29, 2018

Name of Sponsor/Company: Avenue Therapeutics, Inc.
Name of Investigational Product: AVE-901 (Tramadol)
Name of Active Ingredient: Tramadol for intravenous infusion

18. The patient was administered an investigational drug product within 30 days prior to Screening.
 
19. The patient has previously participated in a clinical study with AVE-901.
 
POST SURGICAL EXCLUSION CRITERIA
 
The patient is to be evaluated post-operatively prior to the initial treatment with the study drug and will be withdrawn prior to treatment with the study drug if any of the following exclusion criteria are met:
 
 1. Patients who, in the opinion of the investigator, are not likely to tolerate the protocol's allowed analgesic regimen (tramadol plus non-opioid adjuvants). 2. Patients who have been admitted to the ICU post-surgery or have experienced complications during the surgical procedure that would put them at increased risk from receipt of the investigational product in the opinion of the investigator. 3. The patient is not clinically stable and not able to answer questions and follow commands. 4. The patient has evidence of respiratory insufficiency, such as a respiratory rate that is less than 8 breaths per minute or arterial oxygen saturation by pulse oximetry of less than 90% with supplemental oxygen. 5. Use of 5-HT3 antagonists (e.g. ondansetron, granisetron, palonosetron) preoperatively, intraoperatively, or postoperatively

Investigational product, dosage and mode of administration:
 
AVE-901, 50 mg. Assigned study treatment (51 mL) doses will be administered IV over 15 minutes (+/- 4 minutes) via infusion pump. A trained health care professional will flush the line with normal saline at the end of each infusion.

Duration of treatment:
 
Study drug will be administered for up to 7 days following initiation of the first dose.
 
Total patient participation in this study, from initial screening through the final assessment, is expected to be between 1 and 7 weeks.

Reference therapy, dosage and mode of administration:
 
None.

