
Subgroups
 
Incidences of treatment-emergent AEs, serious AEs, and discontinuations for AEs, will be provided by the following subgroups:
 
 • Surgery type • Gender • Race • Age (using the median age of the treated population) 
Safety
 
All AEs will be classified with respect to the MedDRA System Organ Class (SOC) and preferred term. The number and percent of patients who report treatment-emergent adverse events (TEAEs) will be summarized. Additional summaries by severity, relationship, and subgroup will be presented. Serious AEs (SAEs) will be summarized similarly.
 
For purposes of analysis, TEAEs will be defined as any AE with a start time ‘on or after the start of the first IV infusion’. Thus, the start day AND start time of AEs will be collected. Adverse events occurring prior to the start of the first treatment infusion will be classified as Medical History for the purposes of the analysis. Events occurring > 168 hours (7 days) after the END of the last infusion will be classified as Post-Treatment AEs.
 
As the infusions are given intermittently according to the dosing instructions, an assessment of onset of TEAEs within 1 hour after the start of any infusion will be tabulated separately. The incidence of TEAEs will also be tabulated by infusion number (e.g., Infusion 1, Infusion 2, etc.) to explore the safety profile over multiple doses. Summaries of the time to onset of TEAEs will also be included. Exploratory analyses of use of anti-emetics may be performed.
 
Clinical laboratory, and vital sign data will be summarized descriptively by time point. Local tolerability of the infusion site will be assessed via AE’s.
 
Other safety data presentations will be descriptive in nature, with no formal inferential testing planned.
 
Efficacy
 
Patient Global Assessment at 24 hours, and/or end of treatment

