6.6.4. Treatment Period/Post Surgery

Patients will receive their first dose of study medication (T₀) within 8 hours of meeting the postsurgical eligibility. Treatment is anticipated to occur from Hours 0 up to Hour 168. The latest (last dose) that is allowed is at Hour 164. Patients will be dosed at Hour T₀, T₂, T₄, and then every 4 hours thereafter, for a total of up to 43 doses administered over the 168-hour treatment period. Assessments will have a ± 10 minute window.

Antiemetic treatments (with the exception of Zofran or other 5-HT₃ antagonists) are allowed.

Treatment period assessments include:

- Recording vital signs including: respiratory rate, heart rate, pulse oximetry (SpO₂), temperature, and blood pressure at 0, 0.5, 1, 2, 3, 4, and then every 4 hours thereafter during the first 48 hours. After 48 hours patients continuing treatment should have vitals taken every 8 hours.
- ECGs will be assessed at screening, post-surgery prior to dosing (T₀), and at 20 to 30 minutes after the start of each infusion for the first 24 hours. With the 10-minute window allowed per assessments, the on-treatment ECGs need to be done between 10 to 40 minutes after the start of each dosing infusion.
- Patient Global Assessment at 24 hours
- Adverse events and concomitant medications will be collected as appropriate.
- Following the first dose of study drug, the patient will be allowed to use non-opioid analgesics if additional pain relief is required. These medications will be captured on the concomitant medications page
- Concomitant medication use

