11.5. Reporting Adverse Events

Information about AEs and SAEs will be collected from treatment (i.e. from time of first dose) through the follow-up phone call. AEs or SAEs occurring prior to first dose of study treatment will be considered Medical History. AEs or SAEs occurring during or after the first dose of study treatment will be treatment-emergent (S)AE. Any SAEs considered at least possibly related to the investigational product and discovered by the Investigator at any time after the study should be reported. The Investigator must complete, sign and date the SAE pages, verify the accuracy of the information recorded on the SAE pages with the corresponding source documents.

Additional follow-up information, if required or available, should all be communicated within one business day of receipt and this should be completed on a follow-up SAE form and placed with the original SAE information and kept with the appropriate section of the eCRF and/or study file.

The Sponsor is responsible for notifying the relevant regulatory authorities of certain events. It is the Investigator's responsibility to notify the IRB of all SAEs that occur at his or her site. Investigators will also be notified of all unexpected, serious, drug-related events (7/15 Day Safety Reports) that occur during the clinical trial. Each site is responsible for notifying its IRB or IEC of these additional SAEs.

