12.10.1. Adverse Events

Adverse events will be coded using the MedDRA coding dictionary; patient incidence of each system organ class and unique term will be tabulated. AE incidence will also be tabulated according to relationship to study medication and severity. Serious AEs and AEs resulting in premature discontinuation will be tabulated.

Adverse events starting before the first dose of treatment will be recorded as Medical History. Adverse events starting after the first dose of treatment will be considered treatment-emergent adverse events.

Local tolerability of the infusion site will be assessed for pain, swelling, tenderness, and erythema via AE's.

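### The Day 14 (±2) safety call is timed from the first dose, so patients dosed at or beyond Hour 120 can be called before the synopsis's 168-hour post-infusion adverse event window closes

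*Protocol*

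**What the plan says.** **The call.** The Protocol Synopsis states: "A final safety assessment will be conducted on Day 14 (± 2 days) from the first dose via a telephone call". Protocol 6.6.6 uses the same anchor, with the contact timed "from the first dose via a telephone call to check on general well-being, including spontaneous reports of adverse events and concomitant medications". Table 4 lists the call at Day 14±2, and SAP 2.3.5 and SAP Table 1 repeat the timing.

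**End of collection.** Protocol 11.5: "Information about AEs and SAEs will be collected from treatment (i.e. from time of first dose) through the follow-up phone call". The same section keeps one later route open: the investigator should still report serious adverse events (SAEs) judged at least possibly related that come to light after the study.

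**Length of dosing.** Protocol 6.6.4: "The latest (last dose) that is allowed is at Hour 164", and patients are dosed "for a total of up to 43 doses administered over the 168-hour treatment period". The synopsis and SAP 2.3.4 expect treatment over Hours 0 to 48, with extension to Hour 168 possible. Protocol 6.6.4 gives only the upper limit.

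**AE windows.** There are three:
- Protocol Synopsis, Safety: "Events occurring > 168 hours (7 days) after the END of the last infusion will be classified as Post-Treatment AEs".
- Protocol 12.10.1: "Adverse events starting after the first dose of treatment will be considered treatment-emergent adverse events". No upper limit is given there or in 11.5.
- SAP 9.2: treatment-emergent AEs (TEAEs) are summarised up to 24 hours after the start of the last dose, and later events go into a separate Post-Treatment AE tabulation (SAP Table 14.3.1.2).

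**The concern.** The call is counted from the first dose, but the synopsis window is counted from the end of the last infusion. As treatment lengthens, the window's closing time moves later while the permitted call dates stay fixed. Beyond some treatment length, a site that follows the protocol exactly can close a patient out while the protocol's own window is still open.

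The patients concerned are those with the most doses. In a repeat-dose study whose primary objective is safety, they are the ones whose post-dose course matters most. At stake is whether late events in this group, in particular non-serious events and SAEs judged unrelated, are collected for the full seven days that the synopsis implies. The Post-Treatment AE table is also affected: its observation time per patient is shorter after longer treatment, and the SAP describes no adjustment for that.

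**Working it through.** **Dosing schedule, reproduced.** Doses fall at Hours 0 and 2, then at 4, 8, …, 164. That is 2 + [(164 − 4)/4 + 1] = 2 + 41 = 43 doses, the last at Hour 164. 43 × 50 mg = 2150 mg, which matches the maximum in SAP section 6.

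**Inputs**
- Call: Day 12 to Day 16 from first dose, read as elapsed time: 12 × 24 = 288 h to 16 × 24 = 384 h after T0.
- Infusion length (Protocol Synopsis): "doses will be administered IV over 15 minutes (+/- 4 minutes) via infusion pump", so 0.25 h nominal, 11 to 19 minutes.
- Synopsis window: 168 h after the end of the last infusion.

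**Formula.** Window closes at (start of last dose) + 0.25 + 168. Unobserved time = closing time − call time, if positive.

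**Worst case, last dose at Hour 164.** 164 + 0.25 + 168 = 332.25 h, or 332.25/24 = 13.84 days after T0. Infusions of 11 to 19 minutes give 332.18 to 332.32 h, which makes no practical difference.

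| Call | Hours after T0 | Call minus window close |
|---|---|---|
| Day 12 | 288 | −44.25 h |
| Day 13 | 312 | −20.25 h |
| Day 14 | 336 | +3.75 h |
| Day 15 | 360 | +27.75 h |
| Day 16 | 384 | +51.75 h |

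At Day 12 the unobserved share is 44.25/168 = 26%.

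**Who is exposed to the gap**
- Day 12 call: the window is still open if the last dose starts after 288 − 168 − 0.25 = 119.75 h, so at Hour 120 or later. That is (164 − 120)/4 + 1 = 12 of the 43 scheduled times. At Hour 120 itself the shortfall is only 0.25 h.
- Day 13 call: 312 − 168.25 = 143.75 h, so Hour 144 or later, (164 − 144)/4 + 1 = 6 of 43.
- Last dose at Hour 116: closes at 284.25 h, covered by 3.75 h even at Day 12.
- Last dose at Hour 48: closes at 216.25 h, covered by 71.75 h.

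**The SAP's TEAE window.** It closes at the latest at 164 + 24 = Hour 188, which is 288 − 188 = 100 h before the earliest permitted call.

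**Post-Treatment follow-up under the SAP rule** (call time minus start of last dose minus 24 h)
- Call at 336 h: single dose, 336 − 0 − 24 = 312 h; Hour-164 dose, 336 − 188 = 148 h.
- Across the permitted calls: from 384 − 24 = 360 h down to 288 − 188 = 100 h.

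**The case against.** A reader might infer that late events are under-ascertained in proportion to exposure, and that every comparison of AEs with exposure is therefore biased. The documents do not support that.

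- The 168-hour limit appears only in the synopsis. The SAP's TEAE window closes at least 100 h before any permitted call, so none of its TEAE tables is truncated, including those by infusion number and within one hour of infusion.
- Under the open-ended definition in Protocol 11.5 and 12.10.1, anchoring to the first dose gives every patient the same planned observation from T0, whatever the exposure.
- Under the 168-hour definition the shortfall is not proportional to exposure. It is zero for last doses up to Hour 116, and zero for anyone called at 336 h or later.
- The 44.25 h figure needs two extremes together, the longest treatment and the earliest call.
- There are safeguards. Possibly related SAEs found later remain reportable, Protocol 11.2.1.2 allows longer follow-up of an event, and patients stay confined during dosing and have End of Treatment assessments.
- The Post-Treatment table is descriptive, with no comparator and no testing.

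All of this stands, and it limits the point to late events. It does not close the gap: a compliant call can still precede the end of a window that the protocol states. The later-reporting route does not cover non-serious events or SAEs judged unrelated. Post-Treatment follow-up is also shorter after longer treatment, for a given call day.

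**Conclusion.** The timing gap is real and narrow. It exists for last doses at Hour 120 or later with a Day 12 call, and at Hour 144 or later with a Day 13 call. Its maximum is 44.25 of 168 h. What it touches is late-event ascertainment under the synopsis definition and the Post-Treatment AE table; the SAP's TEAE results are unaffected.

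The number of patients involved is unknown. The synopsis's expectation of Hours 0 to 48 suggests few, but the documents give no count of patients treated to Hour 120.

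The arithmetic assumes that call days are elapsed 24-hour periods from T0 and that infusions take 15 minutes. If Day 14 is a calendar day, a call more than 3.75 h earlier in the day than the T0 clock time would also miss the window for an Hour-164 patient. This is a low-cost improvement and does not threaten the study's main conclusions.

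**What to change.** **Call timing.** In the Protocol Synopsis, Protocol 6.6.6, Table 4, SAP 2.3.5 and SAP Table 1, keep Day 14 ±2 and add: *and not earlier than 168 hours after the end of the last infusion*. Changing the body without the synopsis would create a new conflict.

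**AE windows.** At the same time, reconcile the three definitions (synopsis, 168 h after end of infusion; Protocol 11.5 and 12.10.1, open-ended; SAP 9.2, 24 h after start of last dose), and state which one governs which table. If a window other than 168 h is kept for follow-up, the floor on the call should match it.

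**Calls already made.** List hours from the end of the last infusion to the call, and flag patients called before 168 h.

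**Cost.** A minor amendment with the ethics review that Protocol 14.1 requires, and a narrower call window for patients dosed at or beyond Hour 120. For an Hour-164 dose the earliest call moves from Day 12 to about Day 13.8; calls from 336 h to Day 16 remain available.

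**What it does not do.** Follow-up will still differ between patients. The minimum Post-Treatment follow-up under the SAP rule rises from 100 h to 168 + 0.25 − 24 = 144.25 h, but the maximum stays at 360 h. The Post-Treatment AE table should therefore report length of follow-up alongside incidence.

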7. SELECTION AND WITHDRAWAL OF PATIENTS

7.1. Patient Inclusion Criteria

The following are patient inclusion criteria for this study; each patient must meet all inclusion criteria in order to be enrolled into this study.

1. The patient is male or female 18-75 years of age
2. The patient or legal representative has voluntarily signed and dated an Institutional Review Board (IRB)/Independent Ethics Committee (IEC) approved written informed consent.
3. Female patients must be of non-childbearing potential (surgically sterile or post-menopausal for at least 1 year) or be practicing a highly effective contraception method from consent to at least 7 days after the last dose of study medication. Surgically sterile is defined as status post hysterectomy, bilateral oophorectomy or bilateral tubal ligation. Highly effective contraception methods include: abstinence, vasectomized partner (at least 6 months prior to dosing); double barrier (diaphragm with spermicide; condoms with spermicide); intrauterine device; implanted or intrauterine hormonal contraceptives in use for at least 6 consecutive months prior to study dosing and throughout the study duration; oral, patch, or injected contraceptives in use for at least 3 consecutive months prior to study dosing.
4. Female patients of childbearing potential have a negative pregnancy test (serum human chorionic gonadotropin [HCG]) during screening and a negative pregnancy test (urine) \leq 24 hours prior to surgery, and are not lactating.
5. Patient is undergoing elective surgery and, in the opinion of the investigator, is an appropriate candidate for IV Tramadol for pain management post-operatively.
6. The study patient is willing to be housed in a healthcare facility capable of administering parenteral analgesia for at least 24 after surgery. Treatment may extend through Hour 168 if deemed appropriate.
7. The patient meets definition of American Society of Anesthesiologists (ASA) Physical Class 1 or 2.
8. The patient is willing and able to understand the study procedures to communicate meaningfully with the study personnel, and to comply with the study protocol.

7.2. Patient Exclusion Criteria

The following are patient exclusion criteria for this study; each patient must **not** meet any of these exclusion criteria in order to be enrolled into this study.

1. The patient has current or historical evidence of any clinically significant disease or condition that might place the patient at unacceptable risk due to receiving the study medication, in the opinion of the investigator.
2. The patient has allergy or hypersensitivity (or is intolerant) to opioids or tramadol.

3. The patient has used chronic opioid therapy, defined as ≥ 20 MEQs of morphine per day ≥ 3 days out of 7 days over the past 4 weeks.
4. The patient has a recent (within 2 years) and/or current history of alcohol, opiate or tranquilizer abuse or dependence.
5. The patient is taking herbal or dietary supplements or medications that are moderate or strong inhibitors of CYP2D6 or CYP3A4 (e.g., fluoxetine, paroxetine, amitriptyline, quinidine, ketoconazole, erythromycin, grapefruit juice) or inducers of CYP3A4 (e.g., carbamazepine, rifampin, St. John's Wort) and cannot go through a minimum washout period of 7 days prior to surgery.
6. The patient has a history of epilepsy, is susceptible to seizures.
7. The patient cannot be withdrawn from medications (at least 7 days prior to surgery) that may lower the seizure threshold (e.g. anti-psychotic agents, MAOI inhibitors) or which increase serotonergic tone (e.g. selective serotonin reuptake inhibitors (SSRIs), serotonin norepinephrine reuptake inhibitors (SNRIs), tricyclic antidepressants, triptans, amphetamines).
8. The patient has had a recent (within 6 months) cardiovascular event or clinically significant abnormal ECG finding at screening.
9. The patient has a history of Long QT Syndrome or a relative with this condition
10. The patient has expressed suicidal ideation within the past 3 months or is considered to be at risk of suicide.
11. The patient is morbidly obese (body mass index [BMI] ≥ 40 kg/m²) or has documented sleep apnea requiring CPAP or other treatment.
12. Female patient is pregnant and/or undergoing a pregnancy-related surgery, or breastfeeding.
13. The patient has a history of cardiopulmonary, neurological or psychiatric condition that may confound the assessments of efficacy or safety.
14. The patient has cirrhosis, moderate or severe hepatic impairment or an alanine aminotransferase (ALT) or aspartate aminotransferase (AST) value $> 3X$ upper limit of normal (ULN) at Screening.
15. The patient has severe renal impairment or a serum creatinine value of $> 2x$ upper limit of normal (ULN) at Screening.
16. The patient has potassium, sodium, calcium or magnesium levels outside of the normal range at Screening
17. The patient has a hemoglobin level at screening which, in the judgment of the Investigator, is not suitable for participation in this study.
18. The patient was administered an investigational drug product within 30 days prior to Screening.
19. The patient has previously participated in a clinical study with AVE-901.

